7.5. Electrocardiogram Results

7.5.1. Investigator Electrocardiogram Assessment

The investigators' assessment of ECG results (normal; abnormal, not clinically significant; abnormal, clinically significant) are collected at screening only. A by-subject listing for ECG assessment results will be provided by subject ID number.

7.6. Other Safety Measures

A data listing will be provided for subjects experiencing pregnancy and subjects using/misusing any substances (eg, illicit drug) during the study, respectively. Physical examination was not collected in the eCRF. Therefore, it will not be included in the analysis.

7.7. Subject Subgroup for Safety Endpoints

Incidence of all treatment-emergent AEs will be repeated within each subgroup defined in Section 3.4.2 using the Safety Analysis set. No formal statistical testing is planned.

7.8. Changes From Protocol-Specified Safety Analyses

No change from protocol-specified safety analyses is planned.

8. PHARMACOKINETIC (PK) ANALYSES

8.1. PK Sample Collection

Blood samples will be collected to determine PK (and metabolites, if applicable) in plasma at the following timepoints:

For Treatment Groups 1 and 2:

Plasma PK sampling will occur relative to dosing of LEN at the following time points for all subjects:

- Days 1, 2, and 8:
 - Predose (within 30 minutes of dosing)
 - A single timed PK sample between 1 and 6 hours postdose

█

- At Day 15 and at all visits with SC LEN injections: A single predose PK sample will be collected
- Starting at Week 4 visit, at all visits without SC LEN injections: A single anytime PK sample will be collected.

CCI

█

█

█

For Treatment Group 3:

- Starting at Day 1 visit, a single anytime PK sample will be collected at all study visits

CCI

█

For Treatment Group 4:

- Starting at Day 1 visit, a single anytime PK sample will be collected at all study visits.

Only plasma CCI samples collected through Week 54 last patient last visit (LPLV) date were analyzed and included in the Week 54 interim analysis.

8.2. PK Analyses Related to Intensive PK Sampling

8.2.1. Estimation of PK Parameters

PK parameters will be estimated using Phoenix WinNonlin® software using standard noncompartmental methods. The linear/log trapezoidal rule will be used in conjunction with the appropriate noncompartmental model, with input values for dose level, dosing time, plasma concentration, and corresponding real-time values, based on drug dosing times whenever possible.

All predose sample times before time-zero will be converted to 0.

For area under the curve (AUC), samples BLQ of the bioanalytical assays occurring prior to the achievement of the first quantifiable concentration will be assigned a concentration value of 0 to prevent overestimation of the initial AUC. Samples that are BLQ at all other time points will be treated as missing data in WinNonlin. The nominal time point for a key event or dosing interval (τ) may be used to permit direct calculation of AUC over specific time intervals. The appropriateness of this approach will be assessed by the PK scientist on a profile-by-profile basis.

Pharmacokinetic parameters such as AUC_{τ} , λ_z and $t_{1/2}$ are dependent on an accurate estimation of the terminal elimination phase of drug. The appropriateness of calculating these parameters will be evaluated upon inspection of PK data on a profile-by-profile basis by the PK scientist.

8.2.2. PK Parameters

CCI [REDACTED]

Table 8-2. PK Parameters for Each Analyte

Analyte	Parameters
TAF	AUC_{τ} , AUC_{last} , CL/F , $t_{1/2}$, λ_z , V_z/F , C_{max} , T_{max} , C_{last} , T_{last} , C_{τ}
TAF Week 38	$AUC_{last,ss}$, $t_{1/2}$, λ_z , $C_{max,ss}$, $T_{max,ss}$, $C_{last,ss}$, $T_{last,ss}$, $AUC_{\tau,ss}$, $C_{\tau,ss}$
TFV	AUC_{τ} , AUC_{last} , $t_{1/2}$, λ_z , C_{max} , T_{max} , C_{last} , T_{last} , C_{τ}
BIC Week 38	$AUC_{last,ss}$, $t_{1/2}$, λ_z , $C_{max,ss}$, $T_{max,ss}$, $C_{last,ss}$, $T_{last,ss}$, $AUC_{\tau,ss}$, $C_{\tau,ss}$
TFV-DP	AUC_{last} , C_{max} , T_{max} , C_{last} , T_{last}

8.2.3. Statistical Analysis Methods

Plasma concentration for LEN, TAF, TFV, BIC, and TFV-DP will be listed for all subjects and summarized by nominal time point for subjects in the PK Analysis Set, CCI [REDACTED] by treatment group and analyte.

PK parameters estimated for TAF, BIC, and TFV will be listed for all subjects. CCI [REDACTED]

Summary statistics (n, mean, SD, coefficient of variation [%CV], median, min, max, Q1, and Q3) will be presented for both individual subject concentration data by time point and individual subject PK parameters by treatment group and analyte. Moreover, the geometric mean, 95% CI, and the mean and SD of the natural log-transformed values will be presented for individual subject PK parameter data.

Individual concentration data listings and summaries will include all subjects with concentration data. The sample size for each time point will be based on the number of subjects with nonmissing concentration data at that time point. The number of subjects with concentration BLQ will be presented for each time point. For summary statistics, BLQ values will be treated as 0 at predose and one-half of the lower LOQ for postdose time points.

Individual PK parameter data listings and summaries will include all subjects for whom PK parameter(s) can be derived. The sample size for each PK parameter will be based on the number of subjects with nonmissing data for that PK parameter.

The following tables will be provided for each analyte by treatment group and visit:

- Individual subject concentration data and summary statistics
- Individual subject plasma PK parameters and summary statistics

The following figures may be provided for each analyte by treatment group:

- Mean (\pm SD) concentration data versus time (on linear and semilogarithmic scales)
- Median (Q1, Q3) concentration data versus time (on linear and semilogarithmic scales)

Individual, mean, and median postdose concentration values that are \leq LOQ will not be displayed in the figures and remaining points connected.

PK sampling details by subject, including procedures, differences in scheduled and actual draw times, and sample age will be provided in listings.

The molecular weight of TFV-DP (447.17 g/mol) and the density of 5000 million cells/mL will be used in the conversion of concentration from ng/million cells to $\mu\text{mol/L}$; where the value in ng/million cells * (5000/447.17) results in the value in $\mu\text{mol/L}$ or μM .

$$\frac{ng}{million\ cells} \times \frac{1\ nmol}{447.17\ ng} \times \frac{1\ \mu mol}{1000\ nmol} \times \frac{5000\ million\ cells}{1\ mL} \times \frac{1000\ mL}{L} = \frac{\mu mol}{L} = \mu M$$

8.2.4. Sensitivity Analyses

Sensitivity analysis may be conducted for the key PK analyses if the PK scientist identifies PK data as questionable. The sensitivity analysis will exclude specific data from analyses, if appropriate. If a sensitivity analysis is deemed necessary, a listing of the PK parameter(s) data being excluded, with associated reason(s) provided by the PK scientist, will be generated.

8.2.5. Changes from Protocol-Specified Pharmacokinetic Analyses

No change from the protocol-specified PK analyses is planned.

10. SOFTWARE

SAS® Software Version 9.4. SAS Institute Inc., Cary, NC, USA.

nQuery Advisor(R) Version 7.0. Statistical Solutions, Cork, Ireland.

Phoenix WinNonlin® 7.0 Pharsigh Corporation, Princeton, NJ, USA.

11. SAP REVISION

Revision Date (DD MMM YYYY)	Section	Summary of Revision	Reason for Revision

12. APPENDICES

Appendix 1. Schedule of Assessments

	Screening ^a	Day 1 ^b	Day 2	CCI										
				Day 8	Day 15	Every 6 weeks from Week 4 to Week 28 ±2 Days	Week 38 ±2 Days	Week 54 ±2 Days	Week 64 ±2 Days	Week 80 ±2 Days	Post Week 80 Visits ^c ±6 Days	30, 90, 180 Day Follow-Up ^d	Early Termination ^e	
Written Informed Consent	X													
Obtain demographic information	X													
Medical History	X													
Complete Physical Examination	X	X			X	X ^f		X		X				X
Symptom-Directed Physical Examination			X	X		X ^g	X		X		X	X		
Vital Signs ^h (including weight)	X	X	X	X	X	X	X	X	X	X	X	X	X	X
12-lead ECG (supine)	X													
Height	X													
Hematology ⁱ , Chemistry ^j , Lipid panel ^k , Urinalysis and Urine Chemistry ^l , CD4+ Cell Count	X	X	X	X	X	X	X	X	X	X	X	X	X	X

	Screening ^a	Day 1 ^b	Day 2	CCI	Day 8	Day 15	Every 6 weeks from Week 4 to Week 28 ±2 Days	Week 38 ±2 Days	Week 54 ±2 Days	Week 64 ±2 Days	Week 80 ±2 Days	Post Week 80 Visits ^c ±6 Days	30, 90, 180 Day Follow-Up ^d	Early Termination ^e
Urine Storage Sample		X	X		X	X	X	X	X	X	X	X		X
Serum Pregnancy Test ^m	X													X
Serum FSH ⁿ	X													
Urine Pregnancy Test ^m		X	X		X	X	X	X	X	X	X	X	X	X
HBV, HCV Testing	X													
HIV-1 Genotyping/Phenotyping	X													
Plasma HIV-1 RNA	X	X	X		X	X	X	X	X	X	X	X	X	X
Plasma Storage Sample	X	X	X		X	X	X	X	X	X	X	X	X	X
PK Plasma Collection ^o		X	X		X	X	X	X	X	X	X	X		
CCI														
Oral GS-6207 Dispensation ^s		X	X		X		X	X	X	X	X	X		

[figure not shown]
	Screening ^a	Day 1 ^b	Day 2	CCI	Day 8	Day 15	Every 6 weeks from Week 4 to Week 28 ±2 Days	Week 38 ±2 Days	Week 54 ±2 Days	Week 64 ±2 Days	Week 80 ±2 Days	Post Week 80 Visits ^c ±6 Days	30, 90, 180 Day Follow-Up ^d	Early Termination ^e
Subcutaneous GS-6207 Administration ^f						X	X		X		X	X		
F/TAF Dispensation ^g		X					X	X	X	X	X	X		
TAF Dispensation ^h							X	X	X	X	X	X		
Bictegravir Dispensation ^h							X	X	X	X	X	X		
B/F/TAF Dispensation ^h		X					X	X	X	X				
Study Drug Accountability		X	X		X	X	X	X	X	X	X	X		
QoL Administration ^h		X				X	X		X		X			
Injection Site Reaction Assessment Worksheet ^h						X	X		X		X			
Adverse Events/ Concomitant Medications	X	X	X		X	X	X	X	X	X	X	X	X	X

- a Screening evaluations must be completed within 30 days prior to Day 1
- b Day 1 tests and procedures must be completed prior to administration of the dose of study drug. Participants must begin dosing on the same day as Day 1
- c Assessments will be performed post Week 80 (Week 90, Week 106, Week 116, Week 132, Week 142) and will continue to alternate between every 10 weeks and every 16 weeks with the visit window ±6 days.
- d Participants may be required to return to the clinic for a 30, 90 and 180-Day Follow-Up Visit after Early Termination visit.
- e Within 72 hours of permanently discontinuing study. Counsel participant regarding the importance of continuing a complete ARV therapy in accordance to standard of care and refer participant to an appropriate HIV treatment facility.
- f Complete physical exam is only required at Week 28
- g Symptom directed physical to be completed at Weeks 4, 10, 16, and 22, as necessary
- h Vital signs – blood pressure, pulse, respiration rate, temperature, and weight
- i Hematology: CBC with differential and platelet count

- j Chemistries: Alkaline phosphatase, AST, ALT, GGT, total bilirubin, direct and indirect bilirubin, total protein, albumin, LDH, CPK, bicarbonate, BUN, calcium, chloride, creatinine, glucose, lipase, magnesium, phosphorus, potassium, sodium, and uric acid. eGFR according to the Cockcroft-Gault formula
- k Fasting is not required for the lipid panel
- l Urinalysis and Urine Chemistry: including color & clarity, specific gravity, pH, glucose, ketones, bilirubin, urobilinogen, blood, nitrite, leukocyte esterase and microscopic (if microscopic elements are seen), urine protein, albumin, creatinine, phosphate, calcium, magnesium and uric acid
- m Women will have a serum test performed at Screening. Urine pregnancy test will only be done for women of childbearing potential. In Treatment Groups 1 and 2, urine pregnancy tests should be confirmed to be negative prior to subcutaneous GS-6207 administration. If any pregnancy test is positive, study drug should be immediately interrupted, and participant should come to the site for serum pregnancy test.
- n FSH test is required for women who are <54 years old and have stopped menstruating for ≥ 12 months but do not have documentation of ovarian hormonal failure.
- o PK collection: For Treatment Groups 1 and 2, plasma PK sampling will occur relative to dosing of GS-6207 at Days 1, 2 and 8 predose (within 30 minutes of dosing) and a single timed PK sample between 1 and 6 hours postdose. **CCI** At Day 15 and all visits with SC GS-6207, a single predose PK sample will be collected. Starting at Week 4 and at all visits without SC GS-6207, a single anytime PK sample will be collected. PK sampling will continue at visits past Week 80.
For Treatment Groups 3 and 4 participants, starting at Day 1, a single anytime PK sample will be collected at all study visits.
- [REDACTED]**
- [REDACTED]**
- [REDACTED]**
- s Treatment Group 1 and 2 oral GS-6207 lead in at Day 1, Day 2 and Day 8. Treatment Group 3 will receive oral GS-6207 lead in at Days 1 and 2 and will begin oral daily GS-6207 at Day 3.
- t Treatment Group 1 and 2 Subcutaneous administration at Day 15 and every 26 weeks
- u Treatment Group 1, 2, and 3 F/TAF once daily for 28 weeks starting at Day 1. Treatment Group 3 participants will continue F/TAF until study completion.
- v Treatment Group 1 daily oral TAF to be initiated at Week 28
- w Treatment Group 2 daily oral BIC to be initiated at Week 28
- x Treatment Group 4 daily oral B/F/TAF
- y Prior to completion of other study procedures, participants will complete HIVTSQ12, HIVDQoL, and EQ-ED-5L at Day 1 (except HIVTSQ12), Day 15 (HIVTSQ12 only), Week 4, Week 28, Week 54, Week 80. Injection Acceptability Scale and Numeric Pain Rating Scale to be completed at Day 15, Weeks 28, 54 and 80 (for Treatment Groups 1 and 2 participants only) after SC GS-6207 administration and completion of other study procedures.
- z Provide Injection Site Reaction Assessment Worksheet and instruct the participants to measure and report injection site reactions following the administration of the subcutaneous injections (for Treatment Group 1 and 2 participants only)

Appendix 2. Flowchart of US FDA-defined Snapshot Algorithm(for Naïve Trial)

The following flowchart for US FDA-defined snapshot algorithm is based on the US FDA Guidance on Human Immunodeficiency Virus-1 Infection: Developing Antiretroviral Drugs for Treatment {U. S. Department of Health and Human Services 2015}

* On-treatment data include all data collected up to 1 day after permanent discontinuation of study drug or all available data for subjects who were still on study drug.

Appendix 3. Programming Specification

- 1) If the age from the Day 1 eCRF is not available, age will be calculated as follows:

Only year is provided for the date of birth (DOB). Use July 1 for the month and day.

- a) AGE (years) is calculated from the number of days between the DOB and Study Day 1,
- b) Use the SAS INTCK function to determine the number of “1st-of-month days” (eg, January 1st, February 1st, March 1st) between DOB and Day 1 (inclusive),
- c) Divide the result in (b) by 12,

AGE = the integer of the result in (c),

Age for laboratory test reference range will be based on the age at the sample collection date.

- 2) All screened subjects refer to all subjects who are screened (ie, with non-missing screening date) and have a screening number. For summaries the same subject is counted only once.
- 3) Screen failure subjects are the subjects who were screened and answered “No” for any inclusion criteria or “Yes” for any exclusion criteria regardless of which version of protocol the subject was consent to.
- 4) Subjects in the randomized analysis set are defined as subjects randomized into the study. IXRSRAND is the source to determine whether the subject is randomized (ie, subject with non-missing RGMNDTN in the IXRSRAND dataset), and confirmed by the eCRF ENROLL dataset (ie, ENROLLYN = “Yes” in ENROLL dataset).
- 5) Randomized treatment (ie, TRT01P in ADSL) is derived from IXRSRAND, while actual treatment received (ie, TRT01A in ADSL) is assigned as the randomized treatment if subject took at least 1 dose of study drug and assigned as blank if the subject was never dosed.
- 6) In the disposition table, the reasons for premature discontinuation are displayed in the order as they appear on the eCRF.
- 7) Body mass index (BMI)

BMI will be calculated only at baseline as follows:

$$\text{— BMI} = (\text{weight [kg]}) / (\text{height [meters]}^2)$$

Baseline height and weight will be used for this calculation if available.

8) SAS codes for the treatment comparison for demographics and baseline characteristics tables.

CMH test for nominal variable (Y), the p-value from the general association test should be used for nominal variables:

```
proc freq;
  tables trt * Y /cmh; /*general association test*/
run;
```

CMH test for ordinal variable (Y), the p-value from the row mean score test should be used for ordinal variables:

```
proc freq;
  tables trt * Y / cmh2 ; /*row mean score test*/
run;
```

Kruskal-Wallis test for continuous variable (Y):

```
proc npar1way wilcoxon;
  class trt;
  var Y;
run;
```

9) For race and ethnicity, “Not Permitted”, “Missing”, or “Other” will be excluded from percentage calculation and also excluded for p-value generation for categorical data analysis (eg, CMH test or Kruskal-Wallis test).

10) Study Day 1, Last Dose Date and Last Exposure Date

- a) All the key dates were defined in Section 3.8.1.

11) Study Day 1 and Last Dose Date

- a) All the key dates were defined in Section 3.8.1.
- b) Study Day 1 is defined as the earliest of the dose start dates from any Study Drug Administration eCRF (ie, EX, EX_ARV or EX_IV).
- c) Last Dose Date is defined for subjects who prematurely discontinued study drug according to Study Drug Completion eCRF(ie, SDRGCOMP).
 - i) For subjects who receive SC injection(ie, A subject has data in EX_IV.), the last dose date is defined as the latest nonmissing end date of the study drug used with LEN (ie, the last dose date in EX_ARV).
 - ii) For subjects who do not receive SC injection(ie, A subject has no data in EX_IV.), the last dose date is defined as the earliest of the last dose date of any study drug (ie, the earliest of last dose date in EX or EX_ARV).

- d) Study drug administration: Oral reload will be recorded as an “Unscheduled” visit in the Study Drug Administration eCRF. Subjects with oral reload prior to the 1st dose of SC have “Unscheduled” dosing visits occurred prior to Day 15 visit. Subjects who received a total of 5 tablets of LEN (300 mg) (ie, 2 x 300 mg LEN tablets each for the first 2 days and 1 x 300 mg LEN tablet on the 8th day) prior to “Unscheduled” dosing visits followed by Day 15 visit will be classified as oral reload due to missing scheduled SC dosing. Otherwise, subjects will be classified as oral reload due to missing scheduled oral dosing visit.

12) Adherence to QD Study Drug(s)

- a) Adherence based on 1 study drug(Treatment Groups 1, 2, and 4):

$$\begin{aligned} \text{Adherence (\%)} &= 100 \times \frac{\text{Total No. of pills taken}}{\text{Total No. of pills prescribed}} \\ &= 100 \times \frac{\sum \text{No. of pills taken at each dispensing period for each study drug}^{[1]}}{\sum \text{No. of pills prescribed at each dispensing period for each study drug}^{[2]}} \end{aligned}$$

- b) Adherence based on 2 study drugs(Treatment Group 3):

$$\begin{aligned} \text{Adherence(\%)} &= 100 \times \frac{\text{Total No. of pills taken}}{\text{Total No. of pills prescribed}} \\ &= 100 \times \frac{\sum \sum \text{No. of pills taken at each dispensing period for each drug}^{[1]}}{\sum \sum \text{No. of pills prescribed at each dispensing period for each drug}^{[2]}} \end{aligned}$$

13) Efficacy Analysis

- a) For categorical efficacy response (eg, Subjects with HIV-1 RNA < 50 copies/mL as determined by US FDA-defined snapshot algorithm, M=F, or M=E Analyses): the proportion difference between LEN-containing regimen groups (Treatment Groups 1 to 3) and the B/F/TAF group (Treatment Group 4) and its 95% CIs are calculated based on the MH proportion adjusted by baseline HIV-1 RNA stratum ($\leq 100,000$ vs. $> 100,000$ copies/mL) (see SAP Section 6.2 and 6.3 for details). The following SAS code will be used to compute p-value, where *brnac* is the baseline HIV-1 RNA stratum, *trtgrp* is the treatment, and *response* is the categorical efficacy response.

```
proc freq data=adeff;  
  tables brnac*trtgrp*response/cmh; /*p value from general  
  association*/  
run;
```

- b) All the ANOVA model for continuous efficacy variable (eg, CD4+): The differences in changes from baseline in \log_{10} HIV-1 RNA and CD4+ cell count between treatment groups and the associated 95% CI will be constructed using an ANOVA, including baseline HIV-1 RNA stratum *brnac*, region stratum *region*, and treatment *trtgrp* as fixed effects in the model.

```
proc glm data=adeff;  
  class brnac region trtgrp;  
  model CD4=brnac region trtgrp;  
  lsmeans trtgrp /alpha=0.05 cl pdiff;  
run;
```

14) Listing for US FDA-defined snapshot outcome:

In addition flag the values of HIV-1 RNA < 50 or ≥ 50 copies/mL for virologic outcomes.

Flag the last available HIV-1 RNA value while on treatment for the following categories:

- a) HIV-1 RNA ≥ 50 copies/mL - Discontinued Study Drug Due to Other Reasons and Last Available HIV-1 RNA ≥ 50 copies/mL
- b) No virologic Data - Discontinued Study Drug Due to Other Reasons and Last Available HIV-1 RNA < 50 copies/mL

15) Injection site reaction (ISR)

- a) To summarize ISRs by injection visit, each study drug related ISR will be associated with one injection visit (eg, Day 15 SC injection, Week 28 SC Injection, Week 54 SC injection) based on the start date of the ISR. If the start date of the ISR is on or after a given injection visit date and prior to the next injection visit date, if available, the ISR will be associated with that injection visit.
- b) For ISR summarized by PT:
 - i) For the overall summary (ie, subjects received at least one injection), multiple ISRs with the same PT will only be counted once per subject for each PT.
 - ii) For by visit summary (ie, subjects received injection for a given injection visit), multiple ISRs associated with the injection visit of interest with the same PT will only be counted once per subject for each PT.
- c) For ISR summarized by grade:
 - i) For the overall summary (ie, subjects received at least one injection), the most severe grade based on all ISRs will be used.
 - ii) For by visit summary (subjects received injection for a given injection visit), the most severe grade from all ISRs associated with the injection visit of interest will be used.

16) Concomitant nonstudy-drug ARV medications (ie, ARV medications other than study drug that are taken on or after first dose date) will be flagged in “Antiviral Medication” listings.

17) Graded Laboratory Abnormalities Summary

18) The following labels will be used for treatment-emergent laboratory abnormalities and treatment-emergent Grade 3 or 4 laboratory abnormalities summary tables and listings:

Battery	Lab Test Label Used in I-labtox Listing	Toxicity Direction	Lab Test Label Used in t-labtox Table
Hematology	Hemoglobin (Hb)	Decrease	Hemoglobin (Decreased)
	Neutrophils	Decrease	Neutrophils (Decreased)
	Platelets	Decrease	Platelets (Decreased)
	WBC	Decrease	WBC (Decreased)
Chemistry	Albumin	Decrease	Albumin (Decreased)
	Alkaline Phosphatase	Increase	Alkaline Phosphatase (Increased)
	ALT	Increase	ALT (Increased)
	Amylase	Increase	Amylase (Increased)
	AST	Increase	AST (Increased)
	Bicarbonate	Decrease	Bicarbonate (Decreased)
	Corrected Calcium	Increase	Corrected Calcium (Hypercalcemia)
	Corrected Calcium	Decrease	Corrected Calcium (Hypocalcemia)
	Creatine Kinase (CK)	Increase	Creatine Kinase (Increased)
	Creatinine	Increase	Creatinine (Increased)
	GGT	Increase	GGT (Increased)
	Lipase	Increase	Lipase (Increased)
	Magnesium	Decrease	Magnesium (Hypomagnesemia)
	Phosphate	Decrease	Phosphate (Hypophosphatemia)
	Serum Glucose (Fasting)	Increase	Serum Glucose (Fasting, Hyperglycemia)
	Serum Glucose (Fasting)	Decrease	Serum Glucose (Fasting, Hypoglycemia)
	Serum Glucose (Nonfasting)	Increase	Serum Glucose (Nonfasting, Hyperglycemia)
	Serum Glucose (Nonfasting)	Decrease	Serum Glucose (Nonfasting, Hypoglycemia)
	Serum Potassium	Increase	Serum Potassium (Hyperkalemia)
	Serum Potassium	Decrease	Serum Potassium (Hypokalemia)
	Serum Sodium	Increase	Serum Sodium (Hypernatremia)
	Serum Sodium	Decrease	Serum Sodium (Hyponatremia)
	Total Bilirubin	Increase	Total Bilirubin (Hyperbilirubinemia)
	Urea Nitrogen (BUN)	Increase	Urea Nitrogen (Increased)
Uric Acid	Increase	Uric Acid (Hyperuricemia)	
Uric Acid	Decrease	Uric Acid (Hypouricemia)	
Urinalysis	Urine Glucose	Increase	Urine Glucose (Glycosuria)
	Urine Protein	Increase	Urine Protein (Proteinuria)
	Urine RBC (Quantitative)	Increase	Urine RBC (Hematuria, Quantitative)

19) Clarification for “Pharmacokinetic Sampling Details and Concentrations” listings

- “Sample age” will be added in this listing, defined as the duration in days between sample collection date and assay date, ie, $\text{sample age} = \text{assay date} - \text{sample collection date} + 1$.
- Scheduled PK sampling time for intensive PK samples at predose is 5 mins prior to dosing time.
- SAMTIME is calculated as the duration in hours between the dosing time before sample collected and sample collection time, except for intensive PK samples at predose. SAMTIME for intensive PK samples at predose is calculated as the duration in hours between the dose time on the same day (ie, right after the predose sample collection) and sample collection time.

GS-US-200-4334-Week54-SAP-v1.0

ELECTRONIC SIGNATURES

Signed by	Meaning of Signature	Server Date (dd- <small>MMM</small> - <small>yyyy</small> hh:mm:ss)
PPD	Biostatistics eSigned	26-Oct-2021 19:20:03
PPD	Clinical Pharmacology eSigned	27-Oct-2021 02:47:41
PPD	Clinical Research eSigned	27-Oct-2021 05:36:46

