8.3.1.2. Safety

The primary analysis set for safety analyses is defined as Safety Analysis Set, which includes all participants who are randomized and receive any dose of study drug. Participants who receive treatment other than that intended will be analyzed according to treatment received. All data collected during treatment will be included in the safety summaries.

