8.6. Safety Analysis

For Treatment Groups 1 and 2, all safety data collected on or after the first dose date will be included. For participants who discontinue from the oral GS-6207, only data collected up to 60 days (approximately 5 times the GS-6207 oral dose half-life) after the last dose of the oral GS-6207 will be included. For Treatment Groups 3 and 4, all safety data collected on or after the first dose date and up to 60 days and 30 days, respectively, after the last dose date will be included. All data will be summarized by treatment according to the study drug received. All collected data will be included in data listings.

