3.2. Subject Grouping

For analyses based on the All Randomized Analysis Set or the FAS, subjects will be grouped according to the treatment group to which they were randomized. For all other analyses, subjects will be grouped according to the actual treatment received. The actual treatment received will differ from the randomized treatment only when their actual treatment differs from randomized treatment for the entire treatment duration.

Subjects will be grouped as follows for table summary:

- Treatment Group 1: SC LEN + (F/TAF → TAF)
- Treatment Group 2: SC LEN + (F/TAF → BIC)
- Treatment Group 3: Oral LEN + F/TAF
- Treatment Group 4: B/F/TAF
- Treatment Groups 1 and 2: SC LEN (for all tables unless specified otherwise)
- Treatment Groups 1, 2 and 3: LEN (for all tables unless specified otherwise)

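### The programming rule for actual treatment copies the randomised arm for every dosed subject, so it cannot carry out the SAP's own grouping by treatment received

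*SAP*

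**What the plan says.** SAP 3.2 sets two grouping rules. The first: "For analyses based on the All Randomized Analysis Set or the FAS, subjects will be grouped according to the treatment group to which they were" randomised. The second: "For all other analyses, subjects will be grouped according to the actual treatment received". The second rule covers the Safety and PK sets and the Per-Protocol set that the SAP defines in 3.1.3. SAP 3.2 also says when the two groupings part company: "only when their actual treatment differs from randomized treatment for the entire treatment duration".

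The protocol points the same way for safety. Section 8.3.1.2: "Participants who receive treatment other than that intended will be analyzed according to treatment received". Section 8.6: "All data will be summarized by treatment according to the study drug received".

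SAP Appendix 3 item 5 turns this into variables. "Randomized treatment (ie, TRT01P in ADSL) is derived from IXRSRAND". Actual treatment, TRT01A, "is assigned as the randomized treatment if subject took at least 1 dose of study drug" and is "assigned as blank if the subject was never dosed". There is no third outcome. SAP 7.8 states that the safety analyses do not depart from the protocol.

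**The concern.** Item 5 uses dosing data only to decide whether a subject was dosed, not which regimen was taken. The exception that SAP 3.2 allows therefore cannot arise under the rule meant to implement it.

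The mismatch has substance because the FAS and the Safety Analysis Set have the same members, namely subjects randomised and given at least one dose (SAP 3.1.2 and 3.1.4). Grouping is the only thing that separates them, and item 5 removes it.

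At stake is where a wrongly treated subject's adverse events, laboratory values and drug concentrations are counted. Some safety rules also depend on group:

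- **Last exposure date (SAP 3.8.1).** After early discontinuation, this date closes the treatment-emergent period. It is capped at last dose plus 30 days in Group 4 and plus 60 days in Group 3. In Groups 1 and 2 it is the last study date once an SC injection has been given.
- **Injection site reactions (SAP 7.1.7.1).** These are summarised for Groups 1 and 2 only.

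The SAP does not say that these rules are keyed to TRT01A. If they are, a subject randomised to Group 4 but treated throughout with SC lenacapavir would have a shortened event window and would drop out of the injection site summaries.

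**Working it through.** The plan gives no figure on this point, so the check compares the two rules case by case.

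**Inputs.** Four arms (SAP 1.2); the TRT01P and TRT01A rules (SAP Appendix 3 item 5); the grouping rule and its whole-duration condition (SAP 3.2); arm regimens (Protocol 3.3 and 5.3); planned arm sizes of 50, 50, 50 and 25 (SAP 1.3); dosed numbers of 52, 53, 52 and 25 (Protocol 1.2.2.8).

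**Step 1: enumerate the cases.** 4 randomised arms × 4 received arms × 2 (whole duration or not) = 32 dosed cases. The 4 never-dosed cases make 36.

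| Rule | Dosed cases with TRT01A different from TRT01P |
|---|---|
| Appendix 3 item 5 | 0 of 32 |
| SAP 3.2 | 4 × 3 = 12 of 32 |

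The 12 are the mismatched arm pairs in which the other arm's treatment was taken throughout. These are logical cases, not participants, and carry no probability.

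**Step 2: apply the whole-duration condition literally.** Groups 1 and 2 have the same regimen until Week 28. Groups 1 to 3 all take oral lenacapavir 600 mg plus F/TAF on Days 1 and 2. A swap among Groups 1 to 3 therefore coincides with the randomised regimen for at least part of treatment and does not differ for all of it. That removes 3 × 2 = 6 ordered pairs. The remaining 12 − 6 = 6 all involve Group 4, three in each direction.

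**Step 3: size of one case.** As a share of an arm:

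- planned n = 25: 100/25 = 4.0%
- planned n = 50: 100/50 = 2.0%
- dosed n = 52: 100/52 = 1.92%
- dosed n = 53: 100/53 = 1.89%

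These are shares of a table column. The effect on any particular event rate depends on whether that subject had the event.

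**Step 4: what does not move.** The primary analysis uses the FAS, grouped as randomised, so item 5 does not affect it.

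**The case against.** The strongest reply is that this is an editorial mismatch with no shown effect. SAP 3.2 states the grouping rule in the body of the plan, and nothing says that an appendix line overrides it, so a programmer who followed 3.2 would group correctly. The trial is open label (Protocol 5.1.2) and SC doses are given on site (Protocol 5.3), so a whole-study swap with the oral-only Group 4 would be hard to miss. The documents report no such subject.

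Much of this stands, and it rules out several stronger readings that a reader might infer:

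- **That by-treatment-received analyses are impossible.** Item 5 as written cannot deliver them; the SAP as a whole still calls for them.
- **That the protocol requires this for the Per-Protocol set.** The protocol defines no such set. The requirement comes from SAP 3.2 alone.
- **That any subject given another arm's drug is misplaced because of item 5.** A subject wrongly treated for part of the study stays in the randomised arm under SAP 3.2 too. The protocol wording carries no duration condition, so SAP 3.2 is itself the narrower text, but that is separate from item 5.
- **That nothing would reveal a case.** SAP 4.2 and 4.2.2.2 list drug administration and accountability, including kit identifiers. SAP 4.3 lists important deviations. Protocol 7.7 requires reports of medication errors.

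The reply does not remove the contradiction. Item 5 is the only stated derivation of the variable. Listings help only if someone reads them for this purpose. The matching efficacy and safety denominators in Protocol 1.2.2.8 are not evidence that no swap occurred, because a TRT01A built as in item 5 would make them match in any case.

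**Conclusion.** The concern holds in a limited form. Item 5 cannot implement SAP 3.2 for the Safety, PK and Per-Protocol sets. For safety it also conflicts with Protocol 8.3.1.2 and 8.6, while SAP 7.8 declares no change.

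The practical effect is nil unless a subject took another arm's regimen throughout. Each such subject would put 4.0% of the planned Group 4, or 2.0% of a planned lenacapavir arm, in the wrong column. Restricting the cases mainly to swaps with Group 4 rests on reading the whole-duration condition literally; a looser reading would bring swaps among Groups 1 to 3 back in. This is a minor point worth correcting because it is a stated rule that would give a wrong grouping if such a case arose, and the correction is cheap.

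**What to change.** Rewrite Appendix 3 item 5 so that TRT01A is derived from EX, EX_ARV and EX_IV, the dosing datasets that item 11 already uses, under the SAP 3.2 rule. State a fallback to the randomised arm where dosing records cannot tell the arms apart: Groups 1 and 2 for anyone who stopped before Week 28, and Groups 1 to 3 for anyone with dosing on Days 1 and 2 only. Add a listing of every subject whose TRT01A differs from TRT01P; an empty listing would document that no case arose.

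The cost is a small amount of programming and the need to write the fallback down. Sample size, alpha and the FAS primary analysis do not change.
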